3. ENDPOINTS AND BASELINE VARIABLES: DEFINITIONS AND CONVENTIONS

3.1. Primary Endpoint(s)

- Response based on achieving at least a 4-point improvement in the severity of Peak Pruritus Numerical Rating Scale (PP-NRS) from baseline at Week 2;
- Response based on achieving the Eczema Area and Severity Index (EASI)-90 ($\geq 90\%$ improvement from baseline) at Week 4.
- Detailed descriptions of how the PP-NRS and the EASI scores are derived are provided in [Appendix 6](#) and [Appendix 5](#) respectively.

3.2. Key Secondary Endpoint

- Response based on achieving the EASI-90 ($\geq 90\%$ improvement from baseline) at Week 16.

3.3. Secondary Endpoint(s)

- Response based on achieving a $\geq 90\%$ improvement in the EASI total score (EASI-90) at all other scheduled time points up to Week 26;
- Response based on achieving a $\geq 75\%$ improvement in the EASI total score (EASI-75) at all scheduled time points up to Week 26;
- Response based on Investigator's Global Assessment (IGA) score of clear (0) or almost clear (1) (on a 5-point scale) and a reduction from baseline of ≥ 2 points at all scheduled time points up to Week 26;
- Response based on achieving at least a 4-point improvement in the severity of PP-NRS from baseline at all scheduled time points except Week 2;
- Time from baseline to achieve at least a 4-point improvement in the severity of PP-NRS scale;
- Percent Change from Baseline in the % Body Surface Area (BSA) affected at all scheduled time points;
- Percent Change from Baseline in the SCORing Atopic Dermatitis (SCORAD) at all scheduled timepoints;
- Change from baseline in the Hospital Anxiety and Depression Scale (HADS) at all scheduled timepoints;
- Change from baseline in Dermatology Life Quality Index (DLQI) at all scheduled time points;
- Change from baseline in EuroQol Quality of Life 5-Dimension 5-Level Scale (EQ-5D-5L) at all scheduled time points;
- Change from baseline in Patient-Oriented Eczema Measure (POEM) at all scheduled time points;
- Change from baseline in Medical Outcomes Study – Sleep Scale (MOS-Sleep Scale) at all scheduled time points;
- Change from baseline in Skin Pain NRS at all scheduled time points;
- Medicated topical background therapy-free days.

- DLQI \geq 4 Points Improvement from Baseline Response at all scheduled time points;

3.4. Other Endpoint(s)

Not applicable.

3.5. Baseline Variables

In general, for all analyses, baseline will be defined based on observations collected prior to first dose if dosing time is available. For DLQI, EQ-5D-5L, HADS and POEM, baseline will be defined based on observations collected on or prior to the day of first dose. Baseline values for demographics, medical and other history, atopic dermatitis history will be based on measures collected at Visit 1/Screening visit. Study Day 1 is defined as the day the participant receives first dose of study drug. For purposes of all other analyses including analyses for change from baseline, the baseline value will be defined as measured on Day 1. If a value is missing on Day 1, then the last available observation before Day 1 will be used.

For all analyses described in Section 5.2 where baseline disease severity (IGA = moderate vs severe) is used as a stratum or covariate, if a subject is erroneously enrolled with baseline IGA = mild, they will be considered as moderate IGA in the strata or covariate.

3.6. Safety Endpoints

Safety will be assessed by the spontaneous reporting of AEs, physical examinations, and clinical laboratory results in all participants who receive at least one dose of the investigational product. Unscheduled safety assessments may be performed at any time during the study to assess any perceived safety concerns. Endpoints will be assessed as:

- Incidence of treatment emergent adverse events.
- Incidence of SAEs and AEs leading to discontinuation.
- Incidence of clinical abnormalities and change from baseline in selected clinical laboratory values, ECG measurements, and vital signs.

The safety endpoints will be defined in accordance with Clinical Data Interchange Standards Consortium (CDISC) aligned CaPS (CaPS).

3.6.1. Adverse Events

An adverse event will be considered a Treatment-Emergent Adverse Event (TEAE) if the event started during the effective duration of treatment. All events that start on or after the first dosing day and time / start time, if collected, but before the last dose plus the lag time (28 days) will be flagged as TEAEs. The algorithm will not consider any events that started prior to the first dose date.

3.6.2. Laboratory Data

Below is a list of hematology and clinical chemistry test parameters.

- Hematology: Platelet Count, Red blood cell (RBC) Count, Hemoglobin, Hematocrit; RBC Indices: MCV, MCH, MCHC, RBC Morphology, Reticulocyte Count; White blood cell (WBC) count with Differential (%), (Abs): Neutrophils, Lymphocytes, Monocytes, Eosinophils, Basophils; Coagulation Panel: Prothrombin Time/International Normalized Ratio.
- Clinical Chemistry: Albumin, Alkaline Phosphatase, ALT, AST, Blood urea nitrogen; Calcium, Chloride, Creatine, Creatinine; GGT, Glucose (non-fasting), LDH, Phosphokinase, Phosphorus, Potassium; Sodium, Total CO2 (bicarbonate), Total Protein, Total, indirect, and direct bilirubin, Uric Acid;

3.6.3. Vital Signs, including Height and Weight

Vital sign measurements are oral or tympanic temperature, respiratory rate, pulse rate, and blood pressures.

Height is collected at screening and weight is collected at Screening, Baseline, Week 12 and Week 20 visits.

3.6.4. Physical Examinations

Complete physical examinations consist of assessments of general appearance; skin; head, eyes, ears, nose and throat; mouth, heart; lungs; breast (optional); abdomen; external genitalia (optional); extremities; neurologic function; and lymph nodes.

4. ANALYSIS SETS (POPULATIONS FOR ANALYSIS)

Data for all participants will be assessed to determine if participants meet the criteria for inclusion in each analysis population prior to unblinding and releasing the database and classifications will be documented per standard operating procedures.

For purposes of analysis, the following populations are defined:

Population	Description
Enrolled	All participants who sign the ICD.
Randomly Assigned to Study Intervention	All participants who were randomly assigned to abrocitinib or dupilumab.
Full Analysis Set (FAS)	All randomized participants receiving at least one dose of study intervention. Participants will be analyzed according to the intervention to which they were randomized.
Per-Protocol Analysis Set (PPAS)	All randomized participants receiving at least one dose of study intervention who had no major protocol violations. This set will include participants who:

Population	Description
	
 • Were eligible for the study by way of meeting key inclusion criteria and none of the key exclusion criteria. • met I/E criteria of qualifying age • meet I/E criteria of baseline EASI ≥ 16 • meet I/E criteria of prior qualifying treatment • Had actual, observed EASI scores at Week 16. • Took the correct randomized treatment for at least 80% and at most 120% of the assigned amount until Week 16. • Had no other major protocol violations as determined by the clinical team prior to database lock. A major protocol violation in this context is one that is likely to affect materially the efficacy responses of the patient and will be defined by the clinical team before database is locked and any analysis is performed for this study.
Safety	All participants randomly assigned to study intervention and who take at least 1 dose of study intervention. Participants will be analyzed according to the intervention they actually received.

Unless otherwise specified, all observations after dropout or use of rescue therapy will be censored. In general, for the responder analysis, data after dropout or use of rescue therapy will be defined as “non-responsive” after that point.

[figure not shown]
5. GENERAL METHODOLOGY AND CONVENTIONS

5.1. Hypotheses and Decision Rules

The Type I error rate is set at 5% (two sided). The familywise Type I error rate (for testing the primary and key secondary endpoints) will be strongly controlled at 5% using a sequential testing approach.

The procedure will test all hypothesis sequentially. If one hypothesis is not rejected at the 5% level, then the statistical significance will be not claimed for the subsequent hypotheses testing. The procedure will first test superiority of PP-NRS4 response at Week 2 and then EASI-90 at Week 4 between abrocitinib and dupilumab by CMH test specified in the primary analysis. If both hypotheses are rejected, the procedure will continue to test the NI of EASI-90 at Week 16 between abrocitinib and dupilumab. The 95% CMH weighted confidence interval will be constructed for the response difference and NI will be declared if the lower bound of the confidence interval for the response difference (abrocitinib - dupilumab) is greater than -10%. If the non-inferiority is achieved, the procedure will continue to test superiority of EASI-90 at Week 16 between abrocitinib and dupilumab by CMH test specified in the analysis for the key secondary endpoint.

The following figure illustrates the procedure showing the sequence of the tests.

A sequential, step-down approach with the PP-NRS4 endpoint from Week 2 to earlier time points will be utilized as an additional family of hypothesis tests once statistical significance is demonstrated at Week 2. Specifically, further hypotheses of no difference in PP-NRS4 between abrocitinib and dupilumab will be assessed at Day 15, Day 14, Day 13, Day 12, ..., Day 2, in that order. Any hypotheses after the last Day for which the comparison is significant will not be considered statistically significant. All hypotheses in the sequence will be assessed at the 5% level of significance. Although this will not protect the Type-I error for the family of all possible comparisons, it will provide Type-I error protection for the family of PP-NRS4 comparisons over the first 2 weeks.

5.2. General Methods

In general, for descriptive analyses, number and percent will be presented for binary variables. Number, mean, standard deviation, median, first and third quartiles will be presented for continuous variables. For efficacy measures, descriptive analyses will be provided for PP-NRS and EASI.

Estimates of treatment difference between abrocitinib and dupilumab along with its two-sided 95% confidence interval and p-value will be provided. There will be no claims of statistical significance for treatment comparisons unless an exception is noted in Section 5.1 or Section 6 or any of its subsections.

5.2.1. Analyses for Binary Endpoints

Binary data at each scheduled visit will be analyzed by two approaches: (1) the test of hypothesis (and the p-value) of no difference between two treatment groups will be conducted by the Cochran-Mantel-Haenszel (CMH) statistic adjusting for baseline disease severity (IGA moderate or severe); p-values from the CMH statistic will be used to test the hypothesis of no difference in binary responses between two treatment groups; and (2) the proportion of responders in each treatment group will be reported and differences between two treatment groups will be summarized by the weighted difference and its 95% confidence interval obtained by normal approximation. Specifically, for NI of EASI-90 at Week 16 between abrocitinib and dupilumab, the 95% CMH weighted confidence interval will be constructed for the response difference and NI will be declared if the lower bound of the confidence interval is greater than -10%. The difference in proportions will be calculated within each randomization stratum. The final estimate of the difference in proportions will be a weighted average of these stratum-specific estimates using CMH weights. The CMH weight w_k for stratum k ($k = 1, 2$) is given by,

$$w_k = \frac{\frac{n_{ik} n_{ck}}{n_{ik} + n_{ck}}}{\sum_{j=1}^2 \frac{n_{ij} n_{cj}}{n_{ij} + n_{cj}}}$$

where n refers to sample size, the subscript c refers to the dupilumab group and the subscript i refers the abrocitinib group. The difference is estimated as $\hat{d} = \sum_{k=1}^2 w_k (\hat{p}_{ik} - \hat{p}_{ck})$, where \hat{p} refers to the estimated proportion. An estimate for \hat{p} is obtained as x/n , where x is the number of responders.

Two-sided 95% confidence intervals for the difference (based on a normal approximation) are formed by:

$$\hat{d} \pm 1.96 \sqrt{\sum_{k=1}^2 w_k^2 \left(\frac{\hat{p}_{ik}(1 - \hat{p}_{ik})}{n_{ik}} + \frac{\hat{p}_{ck}(1 - \hat{p}_{ck})}{n_{ck}} \right)}$$

In the above formula, the standard error is $\sqrt{\sum_{k=1}^2 w_k^2 \left(\frac{\hat{p}_{ik}(1 - \hat{p}_{ik})}{n_{ik}} + \frac{\hat{p}_{ck}(1 - \hat{p}_{ck})}{n_{ck}} \right)}$. When the number of responders is zero ($x = 0$), then \hat{p} will be replaced by $0.5/(n + 1)$. This change will be made only for calculating the standard error of \hat{d} and not anywhere else.

The 95% confidence interval for the response rate will also be provided using Wald normal approximation (or the Clopper-Pearson exact method when there are no or all responders in one group).

5.2.2. Analyses for Non-Longitudinal Continuous Endpoints

The non-longitudinal continuous data will be analyzed by ANCOVA (Analysis of Covariance) with treatment as the factor and baseline disease severity as covariates. When

modeling the change from baseline values, the variable for visit will start with the first post-baseline visit, and the actual baseline value will be included as a covariate. At each visit, estimates of least square mean (LSM) values and the LSM differences between treatment groups will be derived from the model. The corresponding p-values and 95% confidence intervals will also be derived from the model.

5.2.3. Analyses for Longitudinal Continuous Endpoints

Mixed-effect, repeated measures (MMRM) models will be used. The fixed effects of treatment, visit, treatment-by-visit interaction and baseline disease severity will be included. Visit will be modeled as a categorical covariate. Unstructured covariance matrix will be assumed for the model errors. Compound symmetry covariance matrix will be used if the model with unstructured covariance doesn't converge.

When modeling the change from baseline values, the variable for visit will start with the first post-baseline visit, and the actual baseline value will be included as a covariate. At each visit, estimates of least square mean (LSM) values and the LSM differences between treatment groups will be derived from the model. The corresponding p-values and 95% confidence intervals will also be derived from the model. Graphs will describe the LSM over time.

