Key Secondary	
 • The non-inferiority test of the key secondary endpoint EASI-90 at Week 16 will be analyzed using the 95% CMH weighted confidence interval adjusted by baseline disease severity group (moderate and severe). NI will be declared if the lower bound of the confidence interval for the response difference (abrocitinib - dupilumab) is greater than -10%. This analysis is based on Estimand 1 composite estimand and on population defined set FAS. • For the superiority test of the key secondary endpoint EASI-90 at Week 16 will be analyzed using the Cochran Mantel Haenszel test adjusted by baseline disease severity group (moderate and severe) similarly to the primary endpoints. This analysis is based on Estimand 1 composite estimand and on population defined set FAS. • Secondary analysis 1: CMH test on population defined set PPAS. • Secondary analysis 2: CMH test on population defined set FAS. This analysis will not consider the use of rescue therapy as an intercurrent event. For participants who drop out for any reason, the response will be defined as “non-responsive” after that point. • Secondary analysis 3: Missing observations will be multiply imputed similarly to secondary analysis 2 of the primary endpoints.
Secondary	
 • The secondary endpoints which are summarized as proportions such as EASI-90 at Week 12, will be analyzed using the same method as for the primary endpoints. This would also apply to any other binary endpoint in the study, such as the proportion of response based on IGA of clear (0) or almost clear (1) and ≥ 2-point improvement from baseline. • For continuous endpoints, a mixed effect model with repeated measures (MMRM) will be used. This model will include the factors (fixed effects) for treatment group, disease severity group, visit, treatment by visit interaction, and relevant baseline value. Within the framework of MMRM, the treatment difference will

Endpoint	Statistical Analysis Methods
	be tested at Week 16, as well as at the other time points by time point specific contrasts from the MMRM model. This analysis is based on Estimand 2 hypothetical estimand and on population defined set FAS. Observations after dropout or use of rescue therapy will be censored.
Exploratory	Will be described in the statistical analysis plan finalized before database lock.

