6.2.2.2. Continuous Endpoints

- Endpoints:
 - Weeks 2, 4, 8, 12, 16, 20 and 26 Percent Change from Baseline in %BSA, SCORAD;
 - Weeks 12, 16 and 26 Change from Baseline in HADS;
 - Weeks 2, 12, 16, 20 and 26 Change from Baseline in DLQI;
 - Weeks 12, 16 and 26 Change from Baseline in EQ-5D-5L, POEM, MOS-Sleep Scale;
 - Weeks 2, 12, 16, 20 and 26 Change from Baseline in Skin Pain NRS.
- Estimand strategy: Estimand 2, hypothetical estimand ([Section 2.1.2](#)).
- Analysis set: FAS ([Section 4](#)). Participants must have observed baseline measure to be included in the corresponding analysis.
- Analysis methodology: MMRM ([Section 5.2.3](#)) including change from baseline or percent change from baseline data from the corresponding weeks.
- Intercurrent events and missing data: drop-out for any reason and use of rescue therapy are the intercurrent events; data after dropout or use of rescue therapy at any time during the treatment period will be set as missing; only observed data will be used.
- Number of participants included in the analysis will be presented for each treatment arm.
- The least square mean (LSM) of change from baseline or percentage change from baseline along with the corresponding 95% confidence interval will be presented for each treatment arm at each specified time points.
- The LSM difference along with the corresponding p-value and 95% confidence interval will be presented for abrocitinib versus dupilumab at each specified time points.

6.2.2.3. Time from baseline to achieve at least a 4-point improvement in the severity of PP-NRS scale

- Analysis set: FAS (Section 4). Participants must have baseline PP-NRS ≥ 4 to be included.
- Analysis methodology: analysis of time to event endpoint (Section 5.2.5).
- Intercurrent events and missing data: PP-NRS observations will first be censored by use of rescue therapy; for all participants who have not experienced the event, their time to event will be right censored at the last available measurement time.
- The number of participants, number and percent of participants censored and participants with PP-NRS4 Response will be provided for each treatment arm.
- Estimated survival curves using the Kaplan-Meier method and number of patients at risk will be displayed graphically for each treatment arm. The 25%, 50% and 75% quartiles with their 95% confidence intervals will also be presented for each treatment arm.

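### The MMRM holds the baseline slope constant across visits; a baseline-by-visit term would recover a small amount of precision for the continuous secondary endpoints at almost no cost

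*SAP*

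**What the plan says.** SAP 5.2.3 builds the MMRM from these terms: "The fixed effects of treatment, visit, treatment-by-visit interaction and baseline disease severity will be included". For change-from-baseline outcomes it adds that "the actual baseline value will be included as a covariate". The first sentence does not mention the baseline value, so the two must be read together. On the errors it says: "Unstructured covariance matrix will be assumed for the model errors", with compound symmetry if that model does not converge.

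Protocol 9.4.1 gives the same list: "treatment group, disease severity group, visit, treatment by visit interaction, and relevant baseline value". The protocol synopsis agrees. Neither document names a baseline-by-visit interaction.

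SAP 6.2.2.2 then reports a contrast at every visit: "The LSM difference along with the corresponding p-value and 95% confidence interval will be presented for abrocitinib versus dupilumab at each specified time points". The visits differ by endpoint:

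- %BSA and SCORAD, as percent change: seven visits, Weeks 2 to 26 ("Weeks 2, 4, 8, 12, 16, 20 and 26 Percent Change from Baseline in %BSA, SCORAD").
- DLQI and Skin Pain NRS, as absolute change: five visits ("Weeks 2, 12, 16, 20 and 26 Change from Baseline in DLQI" for DLQI; the same weeks for Skin Pain NRS).
- HADS, EQ-5D-5L, POEM and MOS-Sleep, as absolute change: Weeks 12, 16 and 26 only.

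Appendix 8.2.3 uses the same model for further endpoints, including a weekly-average PP-NRS over Weeks 1 to 26. Appendix 8.2.5 uses it for ACQ at Weeks 12 and 26, without baseline IGA.

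**The concern.** The model lets the treatment effect and the error covariance vary freely by visit but holds the baseline coefficient constant. For a change score, the slope on baseline depends on how strongly the visit value correlates with baseline and on the spread at that visit. Both can shift over 24 weeks as participants improve. At a visit whose true slope is not the pooled slope, part of the explainable baseline variation stays in the residual and widens that visit's confidence interval.

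What is at stake is the width of intervals for secondary and additional endpoints. The data needed for the better adjustment are already collected.

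**Working it through.** **The plan's own figure.** The documents state no power, SD or sample size for any MMRM endpoint. The nearest stated figure is about 70% power for Week 16 EASI-90 superiority (Protocol 9.2), with 300 per arm and rates of 53% and 43%:

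z = (0.10 × √300 − 1.96 × √(2 × 0.48 × 0.52)) / √(0.43 × 0.57 + 0.53 × 0.47) = (1.732 − 1.385) / 0.703 = 0.494, so power is 68.9%.

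That reproduces, but it concerns a CMH analysis and does not bear on the MMRM.

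**Inputs for this point.** From the documents: the model terms, the visits and 600 participants randomised 1:1. Assumed, because the documents are silent: SDs, slopes, correlation of each visit with baseline, correlation between visits, and complete data.

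**Formula.** Let β_t be the true slope of change on baseline at visit t, s_t² the residual variance given baseline, and S the between-visit covariance given baseline. The pooled slope is b = (1′S⁻¹β) / (1′S⁻¹1). The variance of the contrast under the common slope, relative to visit-specific slopes, is

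ratio_t = 1 + (β_t − b)² × Var(baseline) / s_t².

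**Worked case, seven visits.** Take unit SDs, so that β_t = ρ_t − 1 and s_t² = 1 − ρ_t². Let the correlation with baseline fall linearly from 0.6 at Week 2 to 0.2 at Week 26, with residual correlation 0.8 per 4 weeks. Then b = −0.551.

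- Week 2: β = −0.400, s² = 0.640; 1 + 0.151² / 0.640 = 1.036.
- Week 16: β = −0.633, s² = 0.866; 1 + 0.082² / 0.866 = 1.008.
- Week 26: β = −0.800, s² = 0.960; 1 + 0.249² / 0.960 = 1.06.

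A Monte Carlo check (3,000 trials, 300 per arm, complete data) gave 1.04, 1.01 and 1.06, with no bias in the contrasts.

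**Range.** Largest excess at any visit, over linear or early drift and several between-visit correlations:

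| Correlation with baseline, Week 2 → Week 26 | Largest excess variance |
|---|---|
| 0.4 → 0.4 | 0% |
| 0.5 → 0.4 | 0.3-0.6% |
| 0.5 → 0.3 | 1.3-2.5% |
| 0.6 → 0.3 | 3.4-8.1% |
| 0.6 → 0.2 | 5.7-15.1% |
| 0.7 → 0.1 (extreme) | 16.5-46.8% |

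The worst visit is always the first or the last; which one depends on the assumed pattern.

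**DLQI-like scale, five visits.** Assume baseline SD 7, residual SD 5, and slopes linear in time from −0.45 to −0.80. With exchangeable errors, b is the mean of −0.450, −0.596, −0.654, −0.712 and −0.800, which is −0.6425.

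- Week 2: 1 + 0.1925² × 49/25 = 1.073.
- Week 26: 1 + 0.1575² × 49/25 = 1.049.

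With residual correlation 0.8 per 4 weeks, both are 1.060. With milder slopes, −0.50 to −0.70, the excess at these two visits is about 2%.

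**Weeks 12, 16 and 26 only.** The same slopes (−0.596, −0.654, −0.800) and SDs give 0.2-2.7%.

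**In participants and power.** An excess of 5% corresponds to 600 / 1.05 = 571 participants and lowers 80% power to 78.1%. An excess of 10% corresponds to 545 and 76.2%.

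**The case against.** The case for leaving the model alone has substance. A main-effect baseline with unstructured covariance is a valid, common specification. These endpoints lie outside the testing sequence of SAP 5.1, and SAP 5.2 makes no significance claims for them. No decision turns on the change.

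Four stronger readings are tempting, and the documents do not support them.

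- *Early visits, where onset is judged, lose most.* Onset is judged by Week 2 PP-NRS4, Week 4 EASI-90 and the daily PP-NRS4 step-down, all by CMH, and by time to PP-NRS4 with a log-rank test. The MMRM plays no part, and the last visit can lose as much as the first.
- *About 60 participants are thrown away.* One simulated DLQI-like scenario with drop-out gave 11% excess at Week 2, which is about that many. It is one visit of one assumed scale; the closed form with the same end slopes, linear in time and with complete data, gives 6-7%.
- *All continuous endpoints are affected alike from Week 2.* Four scales have no visit before Week 12. SCORAD and %BSA are percent changes. If improvement is proportional to baseline, percent change is nearly unrelated to baseline at every visit (correlation −0.01 to −0.06 in a simple simulation), so there may be little to gain.
- *The contrasts are biased.* With complete randomised data they are not. A stress case with drop-out tied strongly to baseline in one arm only moved a Week 26 contrast by about 0.26 points, roughly 0.6 of a standard error. That pattern was assumed; the sample size section gives no drop-out rate, and nothing in the documents points to such a pattern.

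The objection also shows that the cost is not uniform: the Week 1 to 26 PP-NRS model would need 25 extra terms beside an already large unstructured covariance. None of this removes the precision gain for the scheduled-visit models.

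**Conclusion.** The point holds as a small, free improvement. Both documents specify one baseline slope across visits. The consequence is some loss of precision at visits whose true slope departs from the pooled one, and none where it matches. For the models starting at Week 2, the excess variance at the worst visit is 0% without drift, about 1-3% with mild drift and roughly 5-15% with strong drift; larger values need extreme drift. It is less for HADS, EQ-5D-5L, POEM and MOS-Sleep and possibly little for the percent-change endpoints. All these sizes rest on assumed slopes, SDs and correlations. Primary, key secondary and onset-of-action results are untouched.

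**What to change.** Before unblinding, add the baseline-by-visit interaction to the fixed effects in SAP 5.2.3. Apply it to the MMRMs in 6.2.2.2, to the scheduled-visit MMRMs in Appendix 8.2.3 and to the ACQ model in Appendix 8.2.5.

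The cost is visits minus one: 6 parameters with seven visits, 4 for DLQI and Skin Pain NRS, 2 for the Week 12/16/26 scales and 1 for ACQ. With 600 participants planned this is negligible for the main endpoints, and if the slopes are in fact equal almost nothing is lost. For the weekly-average PP-NRS model the cost is 26 − 1 = 25, so the SAP can state that this model keeps the main effect if convergence is a concern.

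No new data are needed. Protocol 9.4 lets the SAP modify the outlined analyses and requires an amendment only for major changes to primary or key secondary endpoints, so an entry in the SAP version history is enough.

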5.3.2. Continuous Endpoints

In general, all observations after dropout or use of rescue therapy will be censored first. For non-PRO (patient reported outcome) continuous endpoints measured longitudinally, missing values post-baseline will not be imputed explicitly. For such endpoints, assuming that the missing data mechanism is missing at random (MAR), the data will be analyzed based on a restricted maximum likelihood (REML) using a linear mixed-effect model with repeated measures for these continuous variables ([Section 5.2.3](#)). This model will yield valid inferences in the presence of a missing data mechanism that is MAR. This method is based on Estimand 2 hypothetical estimand.

For the continuous PRO variables such as DLQI, POEM, HADS, and EQ-5D-5L, rules suggested by the developers of these instruments will be followed in calculating the missing

values. If these rules are not enough for imputing a value, then the missing values will be handled in the same way as non-PRO variables.

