Appendix 8.2.3. Continuous endpoints

- Endpoints:
 - Weeks 2, 4, 8, 12, 16, 20 and 26 Change from Baseline in SCORAD (VAS) of Sleep Loss, SCORAD (VAS) of itch
 - Weeks 2, 4, 8, 12, 16, 20 and 26 Percent Change from Baseline in PP-NRS, EASI, EASI (excluding scalp, palms and soles of feet) and %BSA (excluding scalp, palms and soles of feet)
 - Weeks 1~26 Percent Change from Baseline in PP-NRS (based on weekly average)
- Estimand strategy: Estimand 2, hypothetical estimand (Section 2.1.2).
- Analysis set: FAS (Section 4). Participants must have observed baseline measure to be included in the corresponding analysis.
- Analysis methodology: MMRM (Section 5.2.3) including change from baseline or percent change from baseline data from the corresponding weeks.

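### If the unstructured MMRM does not converge, the only fallback is compound symmetry with no robust standard error, which misstates visit-specific intervals whenever variance differs between visits

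*SAP*

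**What the plan says.** SAP section 5.2.3 governs the longitudinal continuous endpoints. Its starting point is: "Unstructured covariance matrix will be assumed for the model errors". Its only fallback is: "Compound symmetry covariance matrix will be used if the model with unstructured covariance" fails to converge. No structure is tried in between. On inference it says: "The corresponding p-values and 95% confidence intervals will also be derived from the model". Neither document names an empirical (sandwich) variance or a degrees-of-freedom method. Protocol section 9.4.1 lists the fixed effects of the model and is silent on covariance. SAP section 5.3.2 specifies REML and adds: "This model will yield valid inferences in the presence of a missing data mechanism that is MAR". It does not restrict that assurance to the unstructured fit.

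The longest series among the study-report endpoints (SAP section 6.2.2.2) has seven visits: "Weeks 2, 4, 8, 12, 16, 20 and 26 Percent Change from Baseline in %BSA, SCORAD". DLQI and Skin Pain NRS have five visits; HADS, EQ-5D-5L, POEM and MOS-Sleep have three. SAP Appendix 8.2.3 sends a much longer series through the same section 5.2.3: "Weeks 1~26 Percent Change from Baseline in PP-NRS (based on weekly average". Appendix 8 as a whole is meant for publications and in-house reports, not the clinical study report.

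Under SAP section 5.2, significance is claimed only where section 5.1 or section 6 makes an exception. None is made for the MMRM endpoints, although their p-values and intervals are reported.

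**The concern.** Compound symmetry forces a single variance on every visit and a single correlation on every pair of visits, here from Week 2 to Week 26. Change and percent change from baseline over six months of active treatment need not behave that way. With no robust standard error, each visit's interval is built from a variance averaged over visits. It is then wrong wherever that visit's own variance differs from the average.

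At stake are the visit-specific intervals and p-values for the secondary and additional continuous endpoints, and the section 5.3.2 assurance about inference under MAR, which a misspecified fallback would not honour. That no robust standard error is intended is an inference from the section 5.2.3 wording and from the absence of any mention elsewhere; the SAP does not say so outright.

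**Working it through.** **Inputs from the documents.** Seven post-baseline visits (SAP 6.2.2.2); 300 participants per arm (SAP 2.2); two-sided 5% level (SAP 5.1); REML (SAP 5.3.2). The documents give no SD, power or coverage figure for any MMRM endpoint, so there is no figure of the plan's own to reproduce.

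**Assumptions.** SD changes linearly over the visits and is equal in the two arms. Covariate adjustment is ignored.

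**Step 1: formula.** With complete data, compound symmetry gives the same difference in means at each visit as the unstructured model, but its standard error uses the average variance:

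- pooled SD = sqrt(mean of SD² over visits)
- SE ratio at visit j = pooled SD / SD at visit j
- actual type I error at visit j = 2 × [1 − Φ(1.96 × SE ratio)]

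**Step 2: SD between 20 and 30 over seven visits.** The SDs are 20, 21.67, 23.33, 25, 26.67, 28.33 and 30. Their mean square is about 636.1, so the pooled SD is 25.2.

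- SD-30 visit: ratio 25.2/30 = 0.841, so the SE is 16% too small and type I error is 9.9% (coverage 90.1%).
- SD-20 visit: ratio 25.2/20 = 1.261, so the SE is 26% too large and type I error is 1.3% (coverage 98.7%).

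The formula uses the set of SDs, not their order. If SD rises from 20 to 30, the last visit runs at 9.9%; if it falls from 30 to 20, the last visit runs at 1.3%.

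**Step 3: range of assumptions, seven visits.**

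| Largest SD ÷ smallest SD | SE ratio, largest-SD visit | Type I error there | SE ratio, smallest-SD visit | Type I error there |
|---|---|---|---|---|
| 1 (constant) | 1.000 | 5.0% | 1.000 | 5.0% |
| 1.25 | 0.902 | 7.7% | 1.128 | 2.7% |
| 1.5 | 0.841 | 9.9% | 1.261 | 1.3% |
| 2 | 0.768 | 13.2% | 1.537 | 0.3% |

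With three visits the error at the largest-SD visit is nearly the same: 7.7%, 9.8% and 12.8% for ratios 1.25, 1.5 and 2.

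**Step 4: simulation.** The settings were 300 per arm, seven visits, a REML compound-symmetry fit and 600 runs per scenario (Monte Carlo error about 0.9 points), with SD constant, rising or falling, and with or without MAR dropout.

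- At SD ratio 1.5, the model-based type I error was 8.8% to 11.3% at the largest-SD visit and 1.0% to 2.0% at the smallest.
- With a sandwich standard error on the same compound-symmetry fit, type I error was 3.7% to 7.5% over all visits and scenarios. GLS with the true covariance gave the same range in the same runs.
- With MAR dropout of about 8% to 14%, differing by arm, compound symmetry gave a bias of up to about 0.03 SD, against under 0.01 SD with the true covariance. The sandwich does not remove this.

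**Step 5: how likely is the fallback?** An unstructured matrix for k visits has k(k+1)/2 parameters: 3 visits, 6; 5 visits, 15; 7 visits, 28; 26 visits, 26 × 27/2 = 351. With about 600 participants, 28 parameters should cause little trouble. The 26-week model is harder: neighbouring weekly averages are likely to be highly correlated, Appendix 8.1.1 sets a week to missing when fewer than four diary days are available, and data after dropout or rescue are also removed.

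**The case against.** The strongest objection concerns direction. A reader might infer that late intervals, and Week 26 in particular, would be too narrow. That requires SD to rise over visits, and the documents do not show it. The opposite is at least as plausible for the percent-change endpoints. Improvement cannot pass −100%. In the phase 2b study the 200 mg group reached −82.6% in EASI at Week 12, with EASI scores improving only until Week 6 (Protocol 2.2.3). Setting data after dropout or rescue to missing may also remove poorer responders from late visits. If SD falls, Week 26 is conservative. This objection stands: only the statement about high- and low-variance visits is supported.

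A reader might also take 9.9% as inflation of the trial's error rate. It is not. The primary and key secondary endpoints use CMH methods, the MMRM endpoints lie outside the sequential procedure, and no significance is claimed for them.

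On likelihood, failure to converge is improbable for the study-report endpoints. For the 26-week model, 351 parameters do not prove failure, since up to 600 × 26 = 15,600 weekly averages could be available; that model was not fitted or simulated here. Failure there is more plausible, not established.

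Finally, the SAP already fixes one deterministic fallback, which limits post hoc choice, and any particular order of structures is a convention. Both points are fair. Neither makes the intervals right once the fallback is used with unequal variances.

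**Conclusion.** The point holds as a conditional one of low severity. If the unstructured model fails and variance differs across visits, the section 5.2.3 rule gives intervals that are too narrow at high-variance visits and too wide at low-variance visits. At the largest-SD visit, type I error is about 7.7% to 13.2% for assumed SD ratios of 1.25 to 2; at the smallest-SD visit it is about 2.7% down to 0.3%. These sizes rest on assumed linear SD profiles. The direction over time is unknown.

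There is no effect if the unstructured model converges, and no error in interval width if SD is constant. The consequence is confined to secondary and additional continuous endpoints without significance claims. The place where the fallback is most likely to be reached is the 26-week PP-NRS model, which lies outside the study report but may be published.

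**What to change.** Amend the fallback sentence in SAP section 5.2.3 so that:

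- before compound symmetry, at least one prespecified structure allowing unequal variances is tried, for example heterogeneous Toeplitz, then heterogeneous AR(1);
- the empirical (sandwich) standard error is used whenever the fitted covariance is not unstructured.

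Both parts are needed. The sandwich corrects interval width but not the small bias under MAR dropout, which the heterogeneous structures are meant to reduce. The exact order matters less than fixing it in advance. The section 5.3.2 statement on valid inference should be read with this in mind.

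The cost is one SAP sentence and a software option. Nothing changes in data collection, sample size or the confirmatory analyses.
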